6.3 Conventions

All data listings, summaries, figures and statistical analyses will be generated using SAS version 9.4 or higher¹.

Summaries will be presented by treatment group for all subjects. Treatment group labels will be displayed as follows:

- Placebo
- Voclosporin
- Overall

Columns to be included within the table shells are as follows:

Demography	Treatment group and overall
Baseline	Treatment group and overall
Disposition	Treatment group and overall
Efficacy	Treatment group
TEAEs	Treatment group
Other safety	Treatment group

Tables of events or medications will be ordered in descending frequency of subjects followed by (where applicable) events for the system organ class (or Anatomical Therapeutic Chemical Classification System [ATC] level 2 for medications) followed by the preferred term. Ordering will be for the voclosporin treatment group first followed by the placebo group and alphabetical thereafter.

Listings will be sorted in the following order: treatment group, subject, parameter, and visit unless otherwise stated. All data will be listed.

Continuous variables will be summarized by the number of non-missing observations, mean, median, standard deviation, and minimum and maximum. For all tabulations of changes from baseline data, the lower and upper 95% confidence limits for the mean for the individual treatments will be given.

QMD Ref: [REDACTED]	Effective: 12Aug2019	Governing QMD: [REDACTED]
Confidentiality Statement		
This document is the property of [REDACTED] and may not be duplicated, copied, altered or removed from company without prior approval from [REDACTED] or in compliance with [REDACTED].		

		Controlled Quality Management Document	
		Sponsor:	Aurinia Pharmaceuticals
		Protocol Number:	AUR-VCS-2016-02
STATISTICAL ANALYSIS PLAN. PHASE 2-3-4			

Categorical variables will be summarized by presenting the frequency and percent. Percentages will be based on the number of non-missing observations out of the subject population unless otherwise specified. For each variable, all categories will be shown. Zero frequencies (but not the percent) within a category will be presented.

6.3.1 Decimal Places

Means, medians and percentiles will be displayed to one more decimal place than the data, dispersion statistics (e.g., standard deviation) will have two more decimal places, and the minimum and maximum will be displayed to the same number of decimal places as reported in the raw data. Percentages will be displayed with one decimal place.

P-values will be quoted to 3 decimal places. P-values < 0.001 will be presented as p<0.001.

6.4 Subject Disposition

Subject disposition will be summarized as follows:

- The number of continuation subjects who entered the study from AURORA 1 and who are in each analysis population will be summarized by treatment group and overall for the ITT population. This summary will be repeated for individual levels of the stratification and blocking variables used in AURORA 1.
- The number of early withdrawals and the reasons for withdrawals will be tabulated by treatment group and overall for the ITT population.
- The number of subjects that discontinue study drug will be presented by treatment group and visit for the ITT population.

6.5 Protocol Deviations

Major protocol deviations will be grouped into categories and summarized by treatment group and overall for the Safety and ITT populations. A listing of protocol deviations will be provided.

6.6 Baseline Comparability

The comparability of treatment groups with respect to subject demographics and baseline characteristics will be assessed in a descriptive manner for the Safety population, but no formal statistical testing will be performed. Similar baseline tables to those presented in AURORA 1 will be presented for the continuation subjects in AURORA 2.

Standard continuous or categorical variable summaries will be presented for the following variables based on the safety population.

QMD Ref: [REDACTED]	Effective: 12Aug2019	Governing QMD: [REDACTED]
Confidentiality Statement		
This document is the property of [REDACTED] and may not be duplicated, copied, altered or removed from company without prior approval from [REDACTED] or in compliance with [REDACTED].		

REF: [REDACTED]

		Controlled Quality Management Document	
		Sponsor:	Aurinia Pharmaceuticals
		Protocol Number:	AUR-VCS-2016-02
STATISTICAL ANALYSIS PLAN. PHASE 2-3-4			

- Demographic data (summarized additionally by country and region)
- Disease history (including eGFR and UPCR measures)
- Medical / Surgical / Systemic Lupus Erythematosus / Renal history

Demography and disease history will also be summarized for the ITT population.

Additionally, baseline comparability will be summarized for subjects who did not continue to AURORA 2.

6.7 Medical History

Medical conditions from AURORA 1 will be presented by treatment group for the safety population. Conditions will be presented by Medical Dictionary of Regulatory Activities (MedDRA) primary system organ class and preferred term.

All variables will also be listed.

Additionally, medical history will be summarized for subjects who did not continue to AURORA 2.

6.8 Prior and Concomitant Medications

Separate tabulations will be produced for prior and concomitant medications presented by treatment group and overall for the safety population. Medications will be summarized using ATC Level 2.

Additionally, prior and concomitant medications will be summarized for subjects who did not continue to AURORA 2.

Prior medications are defined as all medications starting and stopping before the date of first dose of study drug in AURORA 1.

Prior and concomitant medications are defined as both:

- **Concomitant Medications Ongoing at the First Dose of AURORA 1:** medications starting before AURORA 1 and continuing at the time of starting AURORA 1.
- **Concomitant Medications Ongoing at the end of AURORA 1:** medication starting before AURORA 2 and continuing at the time of starting AURORA 2.

Concomitant medications are defined as medications starting on or after the date of first dose of study drug in AURORA 2.

QMD Ref: [REDACTED]	Effective: 12Aug2019	Governing QMD: [REDACTED]
Confidentiality Statement		
This document is the property of [REDACTED] and may not be duplicated, copied, altered or removed from company without prior approval from [REDACTED] or in compliance with [REDACTED].		

REF: [REDACTED]

		Controlled Quality Management Document	
		Sponsor:	Aurinia Pharmaceuticals
		Protocol Number:	AUR-VCS-2016-02
STATISTICAL ANALYSIS PLAN. PHASE 2-3-4			

The following previous LN therapies will also be summarized: MMF, Intravenous Cyclophosphamide, Corticosteroids, Methotrexate, Calcineurin Inhibitors, Biologics, Azathioprine, Antimalarials, other. The responses for these LN therapies are Yes or No.

6.9 Exposure to Study Drug

Overall exposure to study drugs (number of days of exposure to study drugs and mean dose) will be presented for both the safety populations. Exposure will be based on prescribed dose. Exposure will not be summarized by visit but for the overall study duration in AURORA 1 and AURORA 2. Overall study drug exposure will be calculated from the first dose date in AURORA 1 to the last dose date in AURORA 2 plus 1. Care should be taken to not double-count days. It is expected that prescription records will cover each study day between randomization and the end of study (or early termination). Periods of zero dose will be assigned as such.

The following gives an example of a subject with 5 prescription records over the 3-year (1095 day) period.

Final prescription records that detail a zero dose will be removed.

Table 5.1 Exposure calculation example

Start Day	End Day	Dose (bid)	Duration
1	364	3	364 days
365	500	3	136 days
501	600	0	100 days
601	750	2	150 days
751	1095	3	345 days

For the purposes of analysis this subject will have ‘days on treatment’ calculated as 364+136+100+150+345=1095 days. Their mean daily dose will be:

$(364*3 + 136*3 + 100*0 + 150*2 + 345*3) / 1095 = 2.34$ caps BID (converted to 37.03mg per day).

Gaps between dosing records will be counted as a zero dose.

For subjects who are lost to follow-up, and for whom the last dose date from the termination record is unknown, the date of the last available visit will be used as the last dose date.

QMD Ref: [REDACTED]	Effective: 12Aug2019	Governing QMD: [REDACTED]
Confidentiality Statement		
This document is the property of [REDACTED] and may not be duplicated, copied, altered or removed from company without prior approval from [REDACTED] or in compliance with [REDACTED].		
REF: [REDACTED]		

		Controlled Quality Management Document	
		Sponsor:	Aurinia Pharmaceuticals
		Protocol Number:	AUR-VCS-2016-02
STATISTICAL ANALYSIS PLAN. PHASE 2-3-4			

Exposure to study drug will be summarized for the following:

- Voclosporin
- MMF
- Oral Corticosteroids.

Prescribed dose changes at visit intervals and overall will be summarized for voclosporin/placebo and for MMF.

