6.2.9 Exposure to Study Drug

Exposure to study drug will be calculated from the date of last dosing minus the first day of dosing (in AURORA 2) + 1 for each prescribing record. Exposure will be summarized as the number of days on medication and mean daily dose. Mean daily dose will take into account periods where zero dose was prescribed.

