6.10 Treatment Compliance

All unused study treatments (and any empty containers) dispensed to the subject will be returned at each study visit for capsule counts to check compliance. The Investigator will count the returned study treatment and this information will be used to assess subject compliance. Subjects will continue on the same dose they are on at the end of AURORA 1. Each softgel capsule = 7.9 mg. It should be noted that compliance will not be summarized by visit but for the overall study period.

Subject compliance with study drug (voclosporin / placebo) will be summarized by treatment group. Counts of the returned study treatment will be used to assess subject compliance. The study treatment count will be documented in the eCRF and source documentation.

Subject compliance will be calculated as:

$$\text{Compliance (\%)} = \frac{\text{Number of dispensed capsules} - \text{Number of lost or returned capsules}}{\text{Number of prescribed capsules}} * 100$$

Note : dispensed capsules includes those carried over from AURORA 1

The number of prescribed doses (number of doses expected to receive in treatment period) will be calculated as per the exposure calculation.

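### Does the wrong result in the SAP 6.9 dose example, with 6.10 naming no exposure window, put the exposure or compliance summaries at risk?

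*SAP*

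**What the plan says.** Three sections of the SAP bear on this.

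- **Section 6.2.9** (derived data) has exposure "calculated from the date of last dosing minus the first day of dosing (in AURORA 2) + 1 for each prescribing record", and says that zero-dose periods count in the mean daily dose.
- **Section 6.9** (the reported table) presents exposure "for the overall study duration in AURORA 1 and AURORA 2", with overall exposure "calculated from the first dose date in AURORA 1 to the last dose date in AURORA 2 plus 1". It illustrates this with Table 5.1, titled "Exposure calculation example": five prescription records over 1095 days. The formula is written out in full and its result is given as 2.34 "caps BID (converted to 37.03mg per day".
- **Section 6.10** defines compliance as dispensed capsules less lost or returned capsules, divided by prescribed capsules. It says that "compliance will not be summarized by visit but for the overall study period", and for the denominator: "The number of prescribed doses (number of doses expected to receive in treatment period) will be calculated as per the exposure calculation". A note adds that "dispensed capsules includes those carried over from AURORA 1".

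Protocol section 13.5 defines compliance as capsules taken over capsules expected at the prescribed dose, across the subject's participation in the study.

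**The concern.** There are two separate worries.

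First, Table 5.1 is the SAP's only numerical illustration of mean dose. If its answer is wrong, a programmer who checks correct code against it will see a mismatch and may go looking for a fault in the code.

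Second, sections 6.2.9 and 6.9 carry the same heading but start the clock in different studies, and 6.10 points to the exposure calculation without saying which is meant. The 1095-day table is the one labelled as the exposure calculation, and the compliance period in 6.10 is worded much like the 36-month period in 6.9. A programmer could follow those cues to a 36-month denominator while counting only AURORA 2 capsules in the numerator. Adherent subjects would then appear to have missed about a third of their doses.

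**Working it through.** **The example.** The inputs are the five records of Table 5.1 and the 7.9 mg capsule strength given in 6.10.

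| Days | Capsules BID | Duration | Product |
|---|---|---|---|
| 1–364 | 3 | 364 | 1092 |
| 365–500 | 3 | 136 | 408 |
| 501–600 | 0 | 100 | 0 |
| 601–750 | 2 | 150 | 300 |
| 751–1095 | 3 | 345 | 1035 |
| Total | | 1095 | 2835 |

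Each duration agrees with its start and end days, and the printed total of 1095 is reproduced. The printed mean is not:

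- Mean dose = 2835 / 1095 = 2.589, i.e. 2.59 capsules BID.
- In mg per day: 2.589 × 2 × 7.9 = 40.91.
- Ratio of printed to correct: 2.34 / 2.589 = 0.904 and 37.03 / 40.91 = 0.905, so both are about 10% low.

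The two printed values agree with each other, since 37.03 / 15.8 = 2.344. A numerator of about 2.344 × 1095 = 2566 would be needed, which is 269 short of 2835. Other treatments of the same records do not explain it:

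- Zero-dose days dropped: 2835 / (1095 − 100) = 2.85.
- Days 365–1095 only: (408 + 0 + 300 + 1035) / 731 = 1743 / 731 = 2.38.
- Days 365–1095 without zero-dose days: 1743 / 631 = 2.76.

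So the final line is wrong, while everything a programmer would code from is right.

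**The compliance windows.** Take Day 365 as the first AURORA 2 dose. This is an assumption drawn from the record break after Day 364; the table does not say it.

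| Fully adherent subject | AURORA 2 capsules | 36-month prescribed capsules | Mixed ratio | Matched ratio |
|---|---|---|---|---|
| 3 capsules BID throughout | 731 × 6 = 4386 | 1095 × 6 = 6570 | 67% | 4386/4386 = 100% |
| The Table 5.1 subject | 1743 × 2 = 3486 | 2835 × 2 = 5670 | 61% | 3486/3486 = 100% |

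The low figures arise only when the numerator and denominator come from different windows.

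**Which window 6.10 intends.** Four features point to AURORA 2:

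- The carry-over note has a purpose only if counting starts at entry to AURORA 2. In a 36-month count those capsules would already be in the AURORA 1 dispensing total.
- The denominator is tied to the treatment period, and protocol section 4.2 gives this study a treatment duration of 24 months.
- Section 6.10 describes subjects as continuing on their end-of-AURORA 1 dose, which is AURORA 2 dosing.
- Protocol section 13.5 refers to participation in this study, and SAP section 9, which lists changes from the protocol analysis, lists none for compliance.

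On this reading, the reference to the exposure calculation supplies the method (prescribed dose times days for each record, with zero doses included) and not the 36-month window.

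**The case for a change.** The best case for a change is that a SAP should not contain a test case that correct code fails, and that one sentence in 6.10 would settle the window. Both statements are true. The arithmetic slip is beyond dispute and is not a reading fault of the PDF, since the two wrong values agree with each other. Section 6.10 does leave the window unnamed, and its phrase about the overall study period does lean towards 36 months.

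Neither point reaches a result. A programmer who gets 2.59 has the whole formula on the same line and can find the discrepancy with one division. A mixed compliance ratio would show itself at first output review, because fully adherent completers on a constant dose would all cluster near 67%. Sections 6.2.9 and 6.9 are not in real conflict either: the first works by prescribing record, the second is labelled as overall exposure and governs the reported table.

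Two further points have been attached to this one. The end date in 6.9, the last AURORA 2 dose, does not exist for the 140 AURORA 1 subjects who did not continue (SAP 6.1.2). Where they are included, their last AURORA 1 dose is the only possible end date. Section 6.12.1.1 pools events from both studies without naming an exposure denominator, but the opening of the adverse event section is not in the text available here, so nothing can be concluded from that silence.

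**Conclusion.** No change to the plan follows. The slip in the 6.9 example is certain: 2.34 and 37.03 should read 2.59 and 40.91, an understatement of about 10% for a hypothetical subject. It is clerical. The analysis is specified by the formula, inputs and zero-dose rule, all of which are correct, and no table draws on the printed answer.

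The unnamed window in 6.10 is a drafting gap and not a demonstrated error. The text as a whole favours counting dispensed, lost or returned, and prescribed capsules all over AURORA 2, and an analyst would be expected to do so. The 67% and 61% figures need a mismatch that the SAP never instructs, and they also assume that AURORA 2 starts on Day 365.

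Exposure and compliance are supporting summaries here. The primary adverse event estimand in SAP 3.1 is a proportion of subjects and uses neither. The judgement on the compliance window rests on the wording of the two documents; the arithmetic rests only on the printed inputs.

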6.10 Treatment Compliance

All unused study treatments (and any empty containers) dispensed to the subject will be returned at each study visit for capsule counts to check compliance. The Investigator will count the returned study treatment and this information will be used to assess subject compliance. Subjects will continue on the same dose they are on at the end of AURORA 1. Each softgel capsule = 7.9 mg. It should be noted that compliance will not be summarized by visit but for the overall study period.

Subject compliance with study drug (voclosporin / placebo) will be summarized by treatment group. Counts of the returned study treatment will be used to assess subject compliance. The study treatment count will be documented in the eCRF and source documentation.

Subject compliance will be calculated as:

$$\text{Compliance (\%)} = \frac{\text{Number of dispensed capsules} - \text{Number of lost or returned capsules}}{\text{Number of prescribed capsules}} * 100$$

Note : dispensed capsules includes those carried over from AURORA 1

The number of prescribed doses (number of doses expected to receive in treatment period) will be calculated as per the exposure calculation.

6.11 Efficacy Analyses

All the secondary efficacy analyses will be performed on the ITT population using data from the start of AURORA 1 through to the completion of AURORA 2. All statistical tests will be performed using a two-tailed 5% overall significance level, unless otherwise stated. All comparisons between treatments will be reported with 95% confidence intervals for the odds ratio, hazard ratio or difference as applicable.

QMD Ref: [REDACTED]	Effective: 12Aug2019	Governing QMD: [REDACTED]
Confidentiality Statement		
This document is the property of [REDACTED] and may not be duplicated, copied, altered or removed from company without prior approval from [REDACTED] or in compliance with [REDACTED].		
REF: [REDACTED]		Page 23 of 37

		Controlled Quality Management Document	
		Sponsor:	Aurinia Pharmaceuticals
		Protocol Number:	AUR-VCS-2016-02
STATISTICAL ANALYSIS PLAN. PHASE 2-3-4			

6.11.1 Efficacy Endpoint

Renal response is defined as:

- UPCR of ≤ 0.5 mg/mg
- eGFR criteria:
 - eGFR ≥ 60 mL/min/1.73 m² or
 - eGFR < 60 mL/min/1.73 m² with no confirmed decrease $> 20\%$ or
 - eGFR < 60 mL/min/1.73 m² with confirmed decrease $> 20\%$ but with no disease-related or treatment-related eGFR associated AE present at time of assessment
- Received no rescue medication for LN
- Did not receive more than 10 mg prednisone for ≥ 3 consecutive days or for ≥ 7 days in total during the 8 weeks prior to the renal response assessment.

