##### **3.3.2 Secondary Endpoints**

###### **3.3.2.1 Key Secondary Endpoints**

- Proportion of subjects in renal response defined as:
  - UPCR of  $\leq 0.5$  mg/mg
  - eGFR  $\geq 60$  mL/min/1.73 m^2 or no confirmed decrease from baseline in eGFR of  $>20\%$
  - Received no rescue medication for LN (see Section 7.8, [Prohibited Therapy and Concomitant Treatment](#))
  - Did not receive more than 10 mg prednisone for  $\geq 3$  consecutive days or for  $\geq 7$  days in total during the 8 weeks prior to the renal response assessment.
- Subjects who withdraw from the study prior to the response assessment will be defined as non-responders.
- Proportion of subjects in partial renal response defined as a 50% reduction from baseline in UPCR.
- Renal flare as adjudicated by the Clinical Endpoints Committee (CEC).
- Extra-renal flare as adjudicated by the CEC.

- SELENA-SLEDAI scores by visit.
- Change in UPCR, eGFR, urine protein, and serum creatinine from AURORA 1 baseline.

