## 10.2.4 Symptoms of the Disease Under Study

Symptoms and fluctuations in laboratory parameters related to the disease under study will not be classed as AEs as long as they are within the normal day-to-day fluctuation of the disease. An explanation of these circumstances must be written in the source documents.

Worsening of the symptoms or laboratory parameters however, will be recorded as an AE, and clearly marked as worsening or by the subject's worst observed intensity. The Investigator will be required to assess the relationship to disease under study for each AE as related or not related. An AE will not be able to be assessed as related to both disease under study and related to study treatment.

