6.11.2 Efficacy Analysis

6.11.2.1 Proportion of subjects in renal response

The number of subjects that meet all four criteria in the above definition of renal response will be summarized by treatment group. The number of subjects who meet each of the four individual criteria will also be summarized by treatment group. These summaries will be presented for Months 6, 12, 18, 24, 30 and 36. Subjects who withdraw from the study prior to the response assessment will be defined as non-responders. The analysis of overall renal response and each of the components will be conducted on the ITT population using a logistic regression model with terms for treatment, baseline UPCR, biopsy class, MMF use at baseline and region, and renal response (Yes/No) at Months 6, 12, 18, 24, 30 and 36 as the response variable.

The results will be expressed as an odds ratio (and associated two sided- 95% confidence interval [CI]) for voclosporin compared to placebo. Odds ratios greater than unity will mean the odds of response are greater for voclosporin than for placebo and therefore indicate a benefit of the voclosporin treatment arm. The p-value of the treatment effect will also be reported.

The following SAS program will be used for the primary efficacy analysis:

```
proc logistic data = data;
class treatment_arm mmf_use biopsy_class region / param=glm;
model response = treatment_arm mmf_use biopsy_class baseline_upcr region;
run;
```

Listing of renal responders and non-responders will also be provided.

QMD Ref: [REDACTED]	Effective: 12Aug2019	Governing QMD: [REDACTED]
Confidentiality Statement		
This document is the property of [REDACTED] and may not be duplicated, copied, altered or removed from company without prior approval from [REDACTED] or in compliance with [REDACTED].		

REF: [REDACTED]

		Controlled Quality Management Document	
		Sponsor:	Aurinia Pharmaceuticals
		Protocol Number:	AUR-VCS-2016-02
STATISTICAL ANALYSIS PLAN. PHASE 2-3-4			

6.11.2.2 Proportion of subjects in partial renal response defined as a 50% reduction from baseline in UPCR

Change from baseline in UPCR will be calculated as the post baseline measurement minus the AURORA 1 baseline measurement. Percent change from baseline will be calculated as:

$$\text{Percent change from baseline (UPCR_pc)} = \left(\frac{\text{Change from baseline}}{\text{Baseline}} \right) \times 100$$

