6.11.4 Sensitivity Analysis

Not applicable.

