9 CHANGES TO PLANNED PROTOCOL ANALYSIS

Additional analyses will be performed to compare subjects who did not participate in AURORA 2 with those who participated.

Protocol stated: “Subjects who receive treatment from more than 1 arm will be assigned to the Orelvo arm.” And this was updated to “Subjects who receive voclosporin treatment for more than 14 days will be assigned to the voclosporin arm irrespective of the arm they were randomized to”.

Protocol did not mention covariates for MMRM analysis. In addition to baseline covariate the following covariates will be included in the model: biopsy class, MMF use at baseline, region.

QMD Ref: [REDACTED]	Effective: 12Aug2019	Governing QMD: [REDACTED]
Confidentiality Statement		
This document is the property of [REDACTED] and may not be duplicated, copied, altered or removed from company without prior approval from [REDACTED] or in compliance with [REDACTED].		

REF: [REDACTED]

		Controlled Quality Management Document	
		Sponsor:	Aurinia Pharmaceuticals
		Protocol Number:	AUR-VCS-2016-02
STATISTICAL ANALYSIS PLAN. PHASE 2-3-4			

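### The SAP adds an AE-dependent eGFR route to renal response that Section 9 does not declare, and no visible planned table gives the protocol-defined response rate

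*SAP*

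**What the plan says.** Protocol 3.3.2.1 and 13.7.2.1 give the same eGFR component for renal response: eGFR of at least 60 mL/min/1.73 m², "or no confirmed decrease from baseline in eGFR of" more than 20%. Neither place attaches an AE condition.

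SAP 3.2.1 and 6.11.1 keep those two routes and add a third. A subject with eGFR below 60 and a confirmed fall above 20% also passes, "but with no disease-related or treatment-related eGFR associated AE present at time of assessment".

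SAP Section 9, where changes to the protocol's analysis are recorded, has three entries: the comparison of AURORA 2 participants with non-participants, the 14-day rule for assigning subjects to an arm in the safety population, and the MMRM covariates ("Protocol did not mention covariates for MMRM analysis"). The eGFR criterion is not mentioned.

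For outputs, SAP 6.11.2.1 plans a table and logistic model for overall response and for each component: "The number of subjects who meet each of the four individual criteria will also be summarized by treatment group". It adds: "Listing of renal responders and non-responders will also be provided". The section headed "6.11.4 Sensitivity Analysis" is marked as not applicable.

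**The concern.** Renal response is the first-listed key secondary endpoint, and the SAP labels its logistic model as the primary efficacy analysis. Under the SAP, a confirmed loss of renal function can count as response solely because no related AE was on record at that visit. Take a baseline eGFR of 78 that falls to a confirmed 58. The protocol fails this subject; the SAP passes the subject unless a related eGFR AE is present.

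A reader of the planned tables could not tell how many responders came in this way, or in which arm. The arms need not reach this situation equally often. Protocol 1.2.5 reports that in the Phase 2 study, TEAEs of decreased GFR led to permanent discontinuation in 1 placebo subject (1.1%) and 7 low-dose voclosporin subjects (7.9%). That does not show a bias towards voclosporin, since a subject with a related AE still fails. It is a reason to look at the count by arm.

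**Working it through.** **1. Where the two definitions differ.** I take the SAP's fall to be measured from baseline, as in the protocol.

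| eGFR ≥60 | Confirmed fall >20% | Related eGFR AE | Protocol | SAP |
|---|---|---|---|---|
| Yes | either | either | pass | pass |
| No | No | either | pass | pass |
| No | Yes | Yes | fail | fail |
| No | Yes | No | **fail** | **pass** |

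Of the eight combinations of three yes/no conditions, exactly one differs. The SAP's first two routes together equal the protocol criterion, so the third is a pure addition. With the other criteria and the baseline unchanged, the SAP rate in each arm at each visit is at or above the protocol-defined rate. For the example, (78 − 58)/78 = 25.6%, which falls in the differing row when no related AE is present.

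**2. Do the AE rules close the route?**

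- Protocol 10.2.4: "Worsening of the symptoms or laboratory parameters however, will be recorded as an AE", but changes "within the normal day-to-day fluctuation of the disease" are exempt.
- Protocol 10.2.5 allows, rather than requires, a laboratory change to be treated as an AE. The grounds are investigator opinion, a shift from normal to pathological, or further worsening of a value already pathological. The last ground may cover the 78 to 58 example.
- SAP 6.2.16 codes a missing drug relationship as related. It codes a missing disease relationship as related unless the AE is recorded as treatment-related. This helps only where an AE exists.
- SAP 6.12.1 counts an AE as related if either the investigator or the sponsor says so.

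Three cases stay open: a fall with no AE recorded, an AE attributed to neither drug nor disease, and an AE judged not to be present at the assessment. The visible text defines neither which AEs are eGFR-associated nor what presence at the assessment means.

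**3. Possible size.** The documents give no response rates, arm sizes or conversion rate, so this is illustration only. Assumptions: the 216 ITT subjects (SAP 6.1.1) split 108/108, and protocol-defined response is p = 45% on voclosporin and q = 35% on placebo. The third route converts 2 to 6% of all subjects in one arm (108 × 0.02 to 0.06 = 2.2 to 6.5 subjects) and 0.5 to 2% in the other (0.5 to 2.2 subjects), taken in both directions.

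OR = p(1 − q) / [q(1 − p)]

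- Start: 0.45 × 0.65 / (0.35 × 0.55) = 1.519. SE of log OR = √(1/48.6 + 1/59.4 + 1/37.8 + 1/70.2) = 0.279, so the unadjusted Wald 95% CI is 0.88 to 2.63.
- Most favourable to voclosporin: 51% v 35.5% gives 1.891, a difference of 15.5 points.
- Most favourable to placebo: 45.5% v 41% gives 1.201, a difference of 4.5 points.
- Equal conversion of 3%: 48% v 38% gives 1.506, essentially no shift.

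Starting from 40% v 30% (OR 1.556, CI 0.89 to 2.73), the range is 1.210 to 1.941.

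**The case against.** The route is openly prespecified in both the endpoint and the analysis sections of the SAP, and Protocol 13.1 leaves full methods to the SAP. On that view the only firm defect is a missing line in Section 9, which also omits the added region term and Month 6 in the logistic model.

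The affected group is narrow. A subject must meet the UPCR, rescue and steroid criteria and also have a confirmed eGFR fall, and SAP 6.2.2 measures falls from the lowest pre-dose eGFR. Such falls are actively reviewed: Protocol 7.6.1.2 requires contributing factors to be ruled out, a confirmatory measurement and Medical Monitor consultation, so a silent non-recording is less likely. Protocol 7.6.1.1 names causes such as dehydration and NSAID changes, so an eGFR AE related to neither drug nor disease can be genuine. Sites are blinded. eGFR has its own MMRM, slope and listings. The not-applicable label on 6.11.4 may be a template remnant, since 6.11.6 and 6.11.7 carry it too. Some SAP text before the visible part of 6.12.1 is not shown, and table shells might split the eGFR component.

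Much of this stands, and it limits the likely size. It does not close the route, and prespecifying a definition does not show what it does to the result. The points about missing tables and undefined terms apply to the visible text only. The protocol-defined rate could be rebuilt from the responder, eGFR, laboratory and AE listings, but nobody is planned to do so.

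**Conclusion.** The concern holds. The SAP changes the definition of a key secondary endpoint, Section 9 does not say so, and no visible planned table gives the protocol-defined rate or isolates the third-route responders. As written, the component summary treats the eGFR criterion as a whole and so pools all three routes.

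Within each arm the direction is certain: SAP rates cannot be below protocol-defined rates, given the same baseline and other criteria. Neither the direction nor the size of the effect on the treatment comparison can be determined from the documents. Even under the unequal conversions assumed above, the shifted odds ratios stay inside the starting confidence interval. The primary endpoint is safety and no visible decision rule depends on renal response, so this is a worthwhile and inexpensive correction rather than a threat to the trial's main conclusion.

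**What to change.** 1. Keep the three-route definition if there is a reason for it, such as comparability with AURORA 1 data; the documents do not state one. List the change and its rationale in Section 9.
2. In 6.11.4, prespecify the same logistic model for renal response with the protocol's two-route eGFR criterion at every analysed visit, reported beside the SAP version.
3. Tabulate, by arm and visit, the subjects who respond only through the third route.
4. If the SAP text not shown does not already do so, specify which AE terms are eGFR-associated and what counts as present at the assessment.

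The cost is SAP wording, one repeated logistic table and one count table. The downside is two more tables to report, and response rates that may be slightly lower under the protocol definition. Trial conduct and data collection are unaffected.
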